8.4. Data Sources

Providers will complete data abstraction into the eCRF using all structured and unstructured data, including laboratory, pathology, and radiology files from the selected patients' electronic health records.

8.6. Data Management

All study data will be entered into the eCRF. The eCRF is designed to allow providers to efficiently move through the patient chart or electronic medical record (EMR) based on the journey of the patient through the course of their disease. The eCRF conforms to the rules and regulations of the Health Insurance Portability and Accountability Act (HIPAA) of 1996 governing the abstraction and storage of protected health information (PHI). No protected health information will be collected in the course of the chart review or stored in the eCRF.

Physicians will be compensated through an honoraria payment for each completed and validated eCRF. The eCRF is anticipated to take up to 45 minutes per patient to complete, and the rate of payment to providers for participation in this study is \$300/completed and validated eCRF. Participating physicians will be asked to complete the chart review individually, meaning that site research staff or supportive staff will not complete any data abstraction.

Cardinal Health will be responsible for the programming, testing, and hosting of data from submitted eCRFs. Providers will access the eCRF through a secure web-based portal, including during the field testing procedures, with all data stored on encrypted, password protected and HIPAA compliant servers housed within the Cardinal Health electronic data storage infrastructure. Cardinal Health will perform extensive testing of the eCRF to ensure functionality across web-based user environments, looping logic to ensure proper alignment of data-related fields (required responses to certain fields prior to entering data into subsequent field), and other programmatic checks to ensure the reduction of the input of erroneous data (such as specifying maximums for year of birth or initiation of first-line treatment within the dates of the enrollment period). In addition, the eCRF will be field-tested among 4 providers to ensure its functionality, the correct interpretation of the questions in relation to the data points of interest, and the length of time required for

completion for a single patient. The pre-test results will be reviewed by Pfizer with Cardinal Health staff; however, Pfizer will not have access to the individual data collected. Any changes made to the eCRF document as a result of the pre-test will require the resubmission of the eCRF and study protocol to the IRB.

8.6.1. Case Report Forms (CRFs)/Electronic Data Record

As used in this protocol, the term CRF should be understood to refer to either a paper form or an electronic data record or both, depending on the data collection method used in this study.

A CRF is required and should be completed for each included patient. The completed original CRFs are the sole property of Pfizer and should not be made available in any form to third parties, except for authorized representatives of Pfizer or appropriate regulatory authorities, without written permission from Pfizer. Cardinal Health shall ensure that the CRFs are securely stored at the study site in encrypted electronic form and will be password protected to prevent access by unauthorized third parties.

Cardinal Health has ultimate responsibility for the collection and reporting of all clinical, safety, and laboratory data entered on the CRFs and any other data collection forms (source documents) and ensuring that they are accurate, authentic/original, attributable, complete, consistent, legible, timely (contemporaneous), enduring, and available when required. The CRFs must be signed by an authorized staff member of Cardinal Health to attest that the data contained on the CRFs are true. Any corrections to entries made in the CRFs or source documents must be dated, initialed, and explained (if necessary) and should not obscure the original entry.

In most cases, the source documents are the hospital or the physician's chart. In these cases, data collected on the CRFs must match those charts.

In some cases, the CRF may also serve as the source document. In these cases, a document should be available at Cardinal Health and at Pfizer that clearly identifies those data that will be recorded on the CRF, and for which the CRF will stand as the source document.

8.6.2. Record Retention

To enable evaluations and/or inspections/audits from regulatory authorities or Pfizer, Cardinal Health agrees to keep records, including the identity of all participating patients (sufficient information to link records, eg, CRFs and hospital records), all original signed informed consent documents, copies of all CRFs, safety reporting forms, source documents, detailed records of treatment disposition, and adequate documentation of relevant correspondence (eg, letters, meeting minutes, and telephone call reports). The records should be retained by Cardinal Health according to local regulations or as specified in the vendor study contract whichever is longer. The investigator must ensure that the records continue to be stored securely for so long as they are retained.

If Cardinal Health becomes unable for any reason to continue to retain study records for the required period, Pfizer should be prospectively notified. The study records must be transferred to a designee acceptable to Pfizer, such as another investigator, another institution, or to an independent third party arranged by Pfizer.

Investigator records must be kept for a minimum of 15 years after completion or discontinuation of the study or for longer if required by applicable local regulations.

The investigator must obtain Pfizer's written permission before disposing of any records, even if retention requirements have been met.

8.7. Data Analysis

Detailed methodology for summary and statistical analyses of data collected in this study will be documented in a SAP, which will be dated, filed and maintained by the sponsor. The SAP may modify the plans outlined in the protocol; any major modifications of primary endpoint definitions or their analyses would be reflected in a protocol amendment.

Beyond the variables described in [Section 8.3](#), non time-to-event clinical outcomes of interest include the ORR and clinical benefit rate (CBR) (CR+PR+SD lasting >24 weeks). The ORR and CBR will be evaluated according the provider assessed response to therapy.

Additionally, providers will also enter the data of disease progression into the eCRF (or discontinuation due to toxicity or other rationale) as reported in the patient charts. PFS and/or time to progression will be assessed at 6-, 12-, 18-, and 24-month following the initiation of therapy (survival rates will also be reported separately).

All categorical or numeric non time-to-event variables collected from the chart data abstraction or calculated from said data will analyzed using descriptive statistical techniques. For numeric variables, the mean, standard deviation, median, and minimum/maximum will be calculated as appropriate. For categorical variables, frequencies and percentages will be provided. The number of missing or unknown observations will be described for both categorical and numeric variables. The 95% confidence intervals will be provided as a measure of estimated precision when appropriate. Comparisons of categorical variable will be made using Chi-square tests (or Fisher exact test) while the student's T-test (or Wilcoxon rank-sum test), F-test or other non-parametric equivalent test will be used to compare values for numeric variables. Statistical significance will be determined using a two-sided $\alpha=0.05$. For univariate comparisons of proportions, any analysis resulting in less than 5 individuals in any cell will not be performed. Similarly, the minimum number of patients to conduct an analysis comparing means of some continuous variable is 30 patients.

Survival analysis, also called time to event analysis, will be used in the current research to describe duration of stable disease, time to disease progression, and PFS. This method of analysis is employed when non-informative right-censoring of observed time-to-event occurs, as is the case for this study since not all patients will have progressed by the end of the study period, the Kaplan-Meier method (product limit estimator) will be used to generate median estimates of time to events if median time is reached within the population and survival curves will also be generated. In addition to calculating the median survival estimate, the life-table method will be used to estimate progression free rates and PFS at 6-, 12-, 18-, and 24-month following initiation of endocrine-based therapy in the metastatic setting.

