Study Design: This will be a retrospective, observational study with all data used having been collected as a routine part of clinical care. Providers will identify patients meeting the study selection criteria. Providers will be recruited to participate from the Cardinal Health Oncology Provider Extended Network, a community of over 7,000 clinical personnel treating cancer patients in the U.S. Providers who indicated treating patients of interest during a prior feasibility assessment will be asked to participate in the research. Providers will abstract data from his/her patients' medical records into an electronic case report form. Cardinal Health will conduct data verification via telephone and electronic follow-up with providers.

Population: The study will include adult female patients with HR-positive/HER2-negative MBC who were treated with palbociclib+LET as initial endocrine therapy on or after 03 February 2015. Providers will randomly select cases beginning with the earliest palbociclib+LET treated patient at least 3 months following the providers' first use of palbociclib.

CCI [REDACTED]

[REDACTED]

[REDACTED]

Variables: Patient demographics, clinical characteristics, treatments, complete blood count (CBC)/cardiac toxicity monitoring patterns, and clinical outcomes will be collected and analyzed.

Data Source: All data will be collected by the patients' treating physician and entered into the eCRF.

Study Size: This is a descriptive study and sample size calculation is not applicable. The target sample size of female, adult, HR-positive, HER2-negative MBC patients receiving initial endocrine therapy with palbociclib+LET is 200.

CCI [REDACTED]

[REDACTED]

Data Analysis: Descriptive analysis will be conducted to describe patient demographics, clinical characteristics, treatment and monitoring patterns, and clinical outcomes. For PFS and other time to event analyses, Kaplan-Meier methods will be used estimate the time to event accounting for right-censoring.

Milestones:

- Start of data collection: Q1 2019.
- Final study report: Q2 2019.

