7. RESEARCH QUESTION AND OBJECTIVES

The main objective of this study is to describe patient demographics, clinical characteristics, toxicity monitoring, treatment patterns and clinical outcomes among postmenopausal, female, HR-positive, HER2-negative, MBC patients receiving palbociclib+LET as initial endocrine therapy. Demographic and clinical characteristics and outcomes will be presented overall, and among groups for the following three planned primary grouping variables:

1. Visceral vs. non-visceral at the initiation of initial endocrine therapy for MBC.
2. Received prior neo/adjuvant endocrine therapy versus no prior neo/adjuvant therapy.
3. De novo metastatic disease versus ≤ 12 months disease free interval since prior neo/adjuvant treatment versus > 12 months disease free interval since prior neo/adjuvant treatment.

[figure not shown]

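### The rule that drops a comparison of proportions when any cell holds fewer than 5 patients acts on observed counts, so whether a test is reported depends on its result

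*Protocol*

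**What the plan says.** Protocol 8.7 (Data Analysis) sets out the tests for variables that are not time-to-event. For categorical variables: "Comparisons of categorical variable will be made using Chi-square tests (or Fisher exact test"). It gives no condition for choosing between the two. The significance level is 0.05, two-sided. The restriction follows, and it is limited to proportions compared univariately: "any analysis resulting in less than 5 individuals in any cell will not be performed". A companion restriction covers continuous variables: "the minimum number of patients to conduct an analysis comparing means of some continuous variable is 30 patients".

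The same section commits to descriptive output that does not depend on these restrictions: "For categorical variables, frequencies and percentages will be provided", with 95% confidence intervals where appropriate.

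Protocol 7 says characteristics and outcomes will be shown overall and within three grouping variables: visceral status, prior neo/adjuvant endocrine therapy, and a three-level split into de novo disease and shorter or longer disease-free interval. The target is 200 patients on palbociclib plus letrozole. The protocol offers no substitute test, no pooling of categories and no list of omitted comparisons. The visible SAP text (7.1, 7.2, 7.4) neither repeats nor withdraws the rule.

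**The concern.** The rule speaks of an analysis resulting in a number of individuals in a cell. That describes counts seen in the data, not counts expected under the null hypothesis. The usual worry about chi-square is small expected counts, which is a different condition. A table can have a very small observed cell and comfortable expected counts, and this is typical when one group has almost no events and the other has many.

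Two things follow. The decision to test depends on the outcome being tested. And, with the comparison group held fixed, moving one group's count towards zero strengthens the evidence of a difference and then removes the test. The companion rule for means does not behave this way, because a minimum number of patients does not depend on the outcome values.

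At stake is which subgroup differences in uncommon categories carry a p-value. A table without one may be taken for a table with nothing to report.

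**Working it through.** The documents give no power or event figure for this rule, so there is no stated figure to reproduce.

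**Inputs**
- Rule and tests: Protocol 8.7.
- Total sample: 200 (Protocol, Abstract).
- Response counts from the feasibility survey (Protocol 8.5): CR 126, PR 340, SD 232, PD 95, missing 11. They sum to the stated 804.
- Rates: PD 95/804 = 11.8%; CR 126/804 = 15.7%; CR+PR 466/804 = 58.0%; PD or missing 106/804 = 13.2%.
- Subgroup sizes: not given. Sizes of 30, 40, 60 and 100 are assumptions that show the range.

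**Step 1. How the rule sorts tables.** Smallest expected count = smaller row total × smaller column total / N. Example: for 4/100 versus 20/100, 100 × 24 / 200 = 12. P-values are two-sided Fisher. The tables are constructed illustrations with N = 200.

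| Table | Fisher p | Smallest expected | Under the rule |
|---|---|---|---|
| 5/100 vs 20/100 | 0.0022 | 12.5 | tested |
| 4/100 vs 20/100 | 0.0008 | 12.0 | not tested |
| 0/100 vs 20/100 | 0.0000007 | 10.0 | not tested |
| 0/40 vs 30/160 | 0.0010 | 6.0 | not tested |
| 4/40 vs 50/160 | 0.0054 | 10.8 | not tested |
| 5/40 vs 19/160 | 1.0 | 4.8 | tested |

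In the four untested tables every expected count is at least 5, so even chi-square would be acceptable. The last row shows the reverse: the rule passes a table whose smallest expected count is below 5. The rule therefore does not track the condition that matters for chi-square.

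**Step 2. Chance that one subgroup triggers the rule.** For a category with rate p in a subgroup of n, P(X ≤ 4) with X ~ Binomial(n, p). For CR+PR, the chance of fewer than 5 non-responders is added.

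| n | PD (11.8%) | CR (15.7%) | PD or missing (13.2%) | CR+PR (58.0%) |
|---|---|---|---|---|
| 30 | 0.72 | 0.48 | 0.64 | 0.0007 |
| 40 | 0.48 | 0.23 | 0.38 | 0.00001 |
| 60 | 0.15 | 0.03 | 0.09 | below 0.00001 |
| 100 | 0.006 | 0.0002 | 0.002 | below 0.00001 |

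The fourth column stands for absence of clinical benefit if every SD patient passed 24 weeks. That is an assumption; the survey gives no SD durations.

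**Step 3. Dependence on the true difference.** Take two independent binomials, 100 per group. P(suppressed) = 1 − product over the two groups of P(5 ≤ X ≤ n − 5). The rates in the last three rows are assumed.

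| True rates | P(suppressed) | Fisher power | Power still reportable |
|---|---|---|---|
| 11.8% vs 11.8% | 0.01 | 0.03 (type I error) | 0.03 |
| 5% vs 15% | 0.44 | 0.59 | 0.21 |
| 3% vs 15% | 0.82 | 0.82 | 0.09 |
| 2% vs 20% | 0.95 | 0.99 | 0.05 |

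With an even split and equal rates the rule almost never acts. It acts more often as one rate approaches zero, just as a test becomes able to detect the difference.

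**The case against.** The strongest reply is that little is lost. The Abstract states: "This is a descriptive study and sample size calculation is not applicable". The visible objectives all describe, none rests on a subgroup p-value, and Protocol 7 speaks of presenting results among groups rather than testing them. That stands, and it limits the importance of the point. It does not remove it, because Protocol 8.7 does plan tests at a two-sided 0.05 level.

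Four stronger readings are tempting and are not supported:
- **That sparse comparisons vanish, or that the report is biased towards similarity.** Frequencies and percentages are promised separately, so 0/40 beside 30/160 would still be tabulated. Only the test is omitted.
- **That every analysis is affected.** The rule covers univariate comparisons of proportions. Progression-free survival, time to progression and survival use Kaplan-Meier or life-table methods, and the logistic and Cox models in SAP 7.4 are not univariate comparisons of proportions.
- **That the main response endpoint is at risk.** With objective response as CR+PR (SAP 5.4), Step 2 shows a negligible chance at the survey rate.
- **That the protocol contradicts itself by assigning Fisher's test to small counts.** It names the test without saying when it applies, and the 5/40 versus 19/160 table shows that Fisher still has a use under the rule.

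A reader might also infer that a predictor with a sparse cell could not pass the 0.20 univariate screen in SAP 7.4. The documents do not say whether that screen uses the Protocol 8.7 tests.

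Finally, the SAP may modify the protocol's methods and parts of its section 7 are blacked out. The rule may be changed there, or may mainly serve larger cohort comparisons. Nothing visible shows either.

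**Conclusion.** The point holds in a limited form. As written, the rule makes the reporting of a test depend on the result and removes tests from tables in which both Fisher and chi-square would be valid. It gives no protection that a choice by expected counts would not give better.

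The effect falls on p-values for uncommon categories (PD, CR and possibly absence of clinical benefit) in small subgroups. At the survey PD rate it ranges from likely (72% at n = 30) through about even (48% at n = 40) to rare (0.6% at n = 100). These figures rest on three assumptions: subgroup sizes that the documents do not give, survey rates that carry over to the study cohort, and a reading of the rule as referring to observed counts. The differing rates in Step 3 are illustrative. This is worth correcting because the correction is nearly free; it does not threaten the descriptive objectives.

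**What to change.** Replace the rule in Protocol 8.7, and state the same in the SAP, with: *Fisher's exact test is used when any expected cell count is below 5, otherwise chi-square; every planned subgroup comparison of proportions is reported with its proportions and exact 95% confidence intervals.*

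This takes one sentence and needs no further data. The price is that some wide intervals and low-power tests will appear in the tables; the intervals make that imprecision visible.

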8.8. Quality Control

During data collection, Cardinal Health's clinical research staff will review all submitted eCRFs for quality control. Cardinal Health's clinical research team will inspect each submitted eCRF for implausible dates (ie, date of death prior to last date of treatment), non-standard treatments, lab and radiology results which are inconsistent with known clinical parameters, or other clinical data which is inconsistent with known standards and outcomes. Should these items be discovered, Cardinal Health's clinical research team will contact the provider submitting the eCRF for data verification. All providers are informed in their contractual agreement that follow-up with clinical staff at Cardinal Health may be required. Participating providers are asked to create a 4-digit unique identifier code per patient which is provided to Cardinal Health through the eCRF and used for identifying the patient record for verification between Cardinal Health and the provider.

In addition to review of the submitted data by the clinical research team, the study statistician will conduct an analysis of submitted data to identify any data points which are inconsistent (outliers) with the study population average. This analysis will include a descriptive analysis of the provider characteristics, demographics, baseline clinical and disease characteristics, and characteristics of treatment patterns (eg, DOT). Data points flagged as outliers will be delivered to the clinical research team who will contact providers to validate data as previously described.

8.9. Limitations of the Research Methods

The key limitation of this research and research of this nature involving retrospective medical chart review abstraction by a patient's treating providers is the reliance on the provider to accurately complete the eCRF. In order to ensure clarity and consistency in reporting, the eCRF will be internally and externally pre-tested. In addition, clinical data quality review will be conducted for each eCRF and invalid or outlier data will be flagged for further review with the treating clinician by Cardinal Health clinical research staff.

Several other limitations impact the external generalizability the results of this retrospective cohort study. Given that providers abstract data on selected patients there is an opportunity for the following to occur: (1) provider selection bias; (2) patient selection bias; (3) and information bias, related to the availability and quality of data contained within the patient charts.

In terms of the representativeness of the provider cohort by imposing a maximum number of eCRFs which can be completed this bias is reduced. With a maximum of 20 eCRFs, the minimum number of providers participating is 30. While the number of providers to be recruited is not specified, not all providers will submit the maximum number of patients. In past research of this nature, the median number of eCRFs submitted per provider is 10. Based on this assessment, the expected number of providers participating is 60. Providers invited to participate but not participating in the research will not be described.

In this study, the magnitude of a patient selection bias will be assessed by quantifying the number of potentially eligible patients and the number of patients submitted for inclusion by the provider. To address this potential bias, providers may only contribute a maximum of 20 patient eCRFs, of which, no more than 10 eCRFs may be submitted for any single treatment group. Differences between providers submitting fewer than 5 versus more than 5 eCRFs may be explored to assess systematic differences and address the potential selection bias.

In regard to information bias, while providers are asked to consult all available patient records certain elements such as the pharmacy dispensing record, data may not be available directly making it possible that items such as dates of initiation and discontinuation of treatment would be less accurate compared to data obtained from an administrative claims database. Similarly, data points such as date of death will be determined based on patient records; providers are not asked to verify date of death based on the Social Security Administration or commercial entities which collect detailed death data. In all these examples, the data are assumed to be missing at random and inspection of data elements will be used to confirm this hypothesis.

There is also a risk of incomplete data as a result of variable patient follow-up with a single provider. Patients may have initiated care at another provider and transitioned to the provider or practice completing the data abstraction. Patients may also have received care from another provider within the practice at multiple points during the course of their disease management and treatment. Thus, data elements from the prior period may not be captured in the participating physician's EMR or clinical notes and providers abstracting the data may misinterpret the intent of the treating provider's notes. In this study, it is required that the patient submitted for study inclusion has been managed and or seen by the provider submitting the data or at the providers practice in order to minimize these potential biases.

CCI
[REDACTED]

CCI
[REDACTED]

CCI

CCI

CCI

CCI

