8.2.1. Inclusion Criteria

Patients must meet all of the following inclusion criteria to be eligible for inclusion in the study:

1. Diagnosed with locoregional recurrent or metastatic female breast cancer.
2. Pathologically confirmed HR-positive/HER2-negative diagnosis.
3. Received treatment with palbociclib in combination with letrozole as initial endocrine-based therapy for advanced/metastatic breast cancer:
 - a. Initiated treatment with palbociclib at least 3 months following the provider's first use of palbociclib following its FDA approval.
 - b. At least 1 month of follow-up (at least one visit with the provider) after initiation of palbociclib.
4. Postmenopausal (or receiving surgical or medical treatment to induce menopause) at the time of initiation of palbociclib.
5. ≥ 18 year old at initiation of palbociclib.

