8.2.2. Exclusion Criteria

No exclusion criteria will be imposed for the selection of patients.ⁱ

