- d. Treatment patterns includes the distribution of regimens administered, by line, from MBC diagnosis through the end of the medical record
- e. Treatment patterns also includes the sequence of treatments across lines, from MBC diagnosis through the end of the medical record

4) Describe the rate of objective disease response during initial endocrine-based therapy

- a. Tumor response will be classified per provider report for each regimen received during MBC treatment
- b. Tumor response will be classified under a primary response classification as complete response (CR), partial response (PR), stable disease (SD), progressive

disease (PD), and not evaluable (NE), and unknown which comprises any other status

- c. Tumor response will be classified under a secondary response classification as matching the primary classification, but for patients with NE, responses classifiable as “Other Favorable” or “Other Unfavorable”

5) Describe PFS from the initiation of initial endocrine-based therapy

- a. Proportion of patients who are persistent to initial endocrine-based therapy for MBC at 3, 6, 12, 18, and 24 months, with persistence defined as the duration of initial regimen until one of the following events occurs: a regimen change or switch, treatment discontinuation, disease progression, or death.
- b. Landmark PFS at 3, 6, 12, 18, and 24 months
- c. Proportion alive at 3, 6, 12, 18 and 24 months

CCI

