7.2 SURVIVAL ANALYSIS

[figure not shown]
Survival analysis, also called time to event analysis, will be used in the current research to estimate the time to treatment discontinuation, time to progression, and PFS in 1L. This method of analysis is employed when non-informative right-censoring occurs as is the case for this study since not all patients will have discontinued treatment, progressed or died by the end of the study period. The Kaplan-Meier method (product limit estimator) will be used to generate median estimates of time to progression and PFS if median time is reached within the population. Survival curves will also be generated. In addition to calculating the median survival estimate, the life-table method will be used to estimate these time to event outcomes at successive 3 month intervals through 24 months post initiation of 1L.

The following lists the measurements to be conducted using survival analysis techniques:

1. Median time to treatment discontinuation
 - a. Proportion of patients (survival estimate and 95% confidence interval) who are still receiving 1L treatment at 3, 6, 12, 18, and 24 months post 1L initiation
 - b. Event = any treatment discontinuation for any reason, censor = patients who are still on 1L therapy at data cut-off
2. Median time to progression
 - a. Proportion of patients (survival estimate and 95% confidence interval) who are progression free at 3, 6, 12, 18, and 24 months
 - b. Event = any treatment discontinuation for disease progression, censor = patients who are still on 1L therapy or who discontinued therapy for any reason other than disease progression at data cut-off
3. Median progression-free survival
 - a. Proportion of patients (survival estimate and 95% confidence interval) who are progression free and alive at 3, 6, 12, 18, and 24 months

- b. Event = any treatment discontinuation for disease progression or death, censor = patients who are still on 1L therapy or who discontinued therapy for any reason other than disease progression or death at data cut-off
- 4. Proportion of patients alive at 3, 6, 12, 18, and 24 months following 1L initiation
 - a. Event = death, censor = date of last follow-up among patients who are not deceased

CC
I

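### Patients who transfer in after starting palbociclib+LET elsewhere are eligible, yet the time-to-event analyses count them at risk from initiation and no practice-entry date is collected

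*Protocol*

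**What the plan says.** **Eligibility.** Protocol 8.2.1 item 3a sets a calendar condition: "Initiated treatment with palbociclib at least 3 months following the provider's first use of palbociclib following its FDA approval". It does not say who started the individual patient. Item 3b asks for "At least 1 month of follow-up (at least one visit with the provider) after initiation of palbociclib", and that visit can fall at any time after initiation. SAP Table 1 is no tighter. Protocol 8.2.2 adds: "No exclusion criteria will be imposed for the selection of patients".

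**Transfers.** Protocol 8.9 foresees them: "Patients may have initiated care at another provider and transitioned to the provider or practice completing the data abstraction". It treats the consequence as incomplete data, noting that earlier elements may be missing from the abstracting physician's records. Its safeguard is that the patient "has been managed and or seen by the provider submitting the data or at the providers practice".

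**Time origin and analysis.** SAP 2.4 objective 5 is to "Describe PFS from the initiation of initial endocrine-based therapy". SAP 7.2 item 4 reports "Proportion of patients alive at 3, 6, 12, 18, and 24 months following 1L initiation". On incomplete observation, SAP 7.2 says: "This method of analysis is employed when non-informative right-censoring occurs as is the case for this study". The visible text makes no provision for delayed entry.

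**Data collected.** The variable tables in Protocol 8.3 and SAP 5.1 list no date of first visit to the practice and no transfer indicator.

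**The concern.** Take a woman who started palbociclib+LET at another practice and moved to the submitting provider at month 10, alive and still on treatment. She meets every written criterion. SAP 7.2 counts her at risk from month 0, although she could not have been sampled through this provider had she died before month 10. Those ten months are guaranteed survival time and, because she arrived on first-line treatment, guaranteed progression-free time as well. This is separate from the one-month follow-up rule and would remain if that rule were dropped.

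The outputs at stake are landmark PFS, time to progression, time to discontinuation and the proportion alive. Protocol 8.1 gives 24-month PFS as the reason for its patient-selection rule. Protocol 8.9 recognises the missing-data side of transfers but not this one. Without an entry date, the problem can be neither corrected nor bounded once charts are abstracted.

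A second, smaller consequence concerns objectives 2 and 3. The starting dose, first dose change and first-cycle tests of a transferred patient took place elsewhere and may be missing from the abstractor's records.

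**Working it through.** The plan states no figure for this point, so there is none to reproduce. The calculation below is illustrative.

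**Inputs from the documents**
- Curve A: median PFS 24.8 months (Protocol 6, phase III trial).
- Curve B: 64.3% progression-free at 24 months (Protocol 6 and SAP 1, real-world study).
- n = 200 (Protocol abstract and 8.5).

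**Assumed, because the documents are silent**
- Exponential event times.
- A share q of the sample transfers at month L while progression-free, with q from 10% to 30% and L from 3 to 12 months.

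**Formulas**
- Curve A: h = ln 2 / 24.8, so S(24) = exp(−24h) = 51.1%. Curve B: h = −ln(0.643)/24.
- A patient who is event-free at L contributes S(24)/S(L), not S(24).
- Unadjusted estimate = (1 − q)·S(24) + q·S(24)/S(L), so bias = q·[S(24)/S(L) − S(24)].

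| q, L | A: S(24)/S(L) | A: bias (points) | B: S(24)/S(L) | B: bias (points) |
|---|---|---|---|---|
| 10%, 3 mo | 55.6% | +0.4 | 67.9% | +0.4 |
| 10%, 6 mo | 60.5% | +0.9 | 71.8% | +0.8 |
| 10%, 12 mo | 71.5% | +2.0 | 80.2% | +1.6 |
| 20%, 12 mo | 71.5% | +4.1 | 80.2% | +3.2 |
| 30%, 12 mo | 71.5% | +6.1 | 80.2% | +4.8 |

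Example, curve A at 20% and month 12: 0.20 × (0.715 − 0.511) = 0.041.

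**Scale.** The 95% CI half-width without censoring is 1.96·√[S(1 − S)/200]: 6.9 points for A and 6.6 for B.

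**Transfers after progression.** These patients also meet the criteria. If their progression came before month 24, they contribute 0 to 24-month PFS. Suppose 10% transfer progression-free at month 12 and 4% transfer after progressing. Curve A then gives 0.86 × 0.511 + 0.10 × 0.715 + 0.04 × 0 = 0.511, so the two effects cancel. A larger share of post-progression transfers would make the net bias negative.

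**Survival.** No 24-month survival figure is given, so 70% to 90% is assumed. The same formula gives +0.1 points (90%; q = 10%, L = 3) to +4.1 points (70%; q = 30%, L = 12).

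**Does delayed entry repair it?** In a simulation of 200,000 patients on curve A, with progression-free transfer times drawn over 0 to 12 months and right-censoring, the 24-month results against a true 51.1% were:

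| q | Ordinary Kaplan-Meier | Delayed-entry Kaplan-Meier |
|---|---|---|
| 10% | 52.0% | 51.1% |
| 20% | 53.0% | 51.1% |
| 30% | 53.7% | 50.9% |

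The simulation makes transfer time independent of prognosis.

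**The case against.** **Transfers on treatment are inferred.** The sentence in Protocol 8.9 speaks of care in general and could mean earlier diagnosis or adjuvant treatment. Protocol 8.1 ties the start of selection to the provider's own first prescription, which points towards patients the provider started. This stands in part: nothing shows that on-treatment transfers will be common. But no visible criterion excludes them. The eligibility questionnaire mentioned in SAP 4 is not shown, so it cannot be assumed to do so.

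**The PFS direction is not fixed.** A reader might infer that PFS and time to discontinuation are necessarily inflated. The documents do not support that, because the same criteria admit women who arrive after progressing on, or stopping, first-line treatment. This objection stands in full.

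**Early data are not necessarily lost.** A reader might also infer that pre-transfer dosing and monitoring are absent from the chart, or that outside tests will be recorded as not done. Protocol 8.9 says only that such data may be missing, and providers are asked to consult all available records. SAP 2.2 offers unknown or missing options, SAP 5.2 monitors the proportion of such responses, and SAP 7.1 reports their number. The supportable statement is possible loss of information, not systematic misclassification.

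**The size may be trivial.** With few, early transfers the bias is under 1 point, well inside sampling error. That is fair. But bias does not shrink with sample size, and without an entry date nobody could show that it was trivial.

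**Conclusion.** The gap is real. The criteria admit patients who started palbociclib+LET elsewhere, the clock starts at initiation, only right-censoring is handled, and the date needed for a correction is not collected.

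- **Proportion alive:** biased upward, because every such patient had to be alive at transfer. This takes transferred patients to have otherwise similar prognosis.
- **PFS and time to discontinuation:** upward from patients transferring progression-free on first-line treatment, possibly downward from those transferring after progression or stopping. The net direction depends on a mix that the documents do not give.
- **Size:** unknown. With progression-free transfers only, 24-month PFS is overstated by about 0.4 to 1 point for few, early transfers and about 3 to 4 points if 20% transfer at month 12, against a CI half-width of about 7 points. These figures rest on assumed shares and timing and on the exponential form.
- **Early dosing and monitoring:** may be incomplete for these patients, not certainly absent.

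It is worth changing because the change is cheap now and cannot be made later from the listed data.

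**What to change.** Choose one of the following before data collection.

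1. **Restrict.** Add to Protocol 8.2.1 item 3, SAP Table 1 and the eligibility screen: *palbociclib+LET was initiated at the submitting provider's practice*.
2. **Keep transfers and adjust.** Abstract the date of first visit to the practice. In SAP 7.2, enter each patient into the risk sets at the later of first-line initiation and that date. Patients whose event preceded entry do not contribute to that outcome. State the assumption that transfer time is independent of prognosis, and run a sensitivity analysis excluding transfers. Limit the starting-dose and early-monitoring summaries to patients whose first cycles are documented, and report that denominator.

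**Cost.** Option 1 needs one criterion and one screening question. It gives a somewhat smaller pool and slightly less inclusive sampling, which weighs against the aim of a representative cohort. The feasibility count of 804 patients for a target of 200 suggests room, but those patients were reported as treated in the past year and were not screened for where treatment began. Option 2 needs one extra data field and a few lines in the SAP.
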